#### *Missing data handling*

Although researchers will take efforts to avoid missing data (e.g., a financial incentive for completing the study and reminder emails), it is not necessary to impute missing data before performing a longitudinal mixed-model analysis (Twisk et al., 2013). Participants with missing data at some assessments will be included in the analysis and results will be modeled on the basis of the available data. For all analyses, the standard  $p < 0.05$  criterion will be used to determine statistical significance.

To test for faulty randomization, researchers will use chi-squared tests on demographic and outcome variables with Yates's continuity correction and t-tests with Welch's approximation of degrees of freedom and assuming unequal variance. If any faulty randomization effects are found, researchers will adjust for them using the confounding variable as a covariate in model testing and will consider them in interpretation of results. These tests will also be used to check for differential dropout.

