### *Missing data handling*

Although the researchers take efforts to avoid missing data (e.g., a financial incentive for completing the study and reminder emails), it is not necessary to impute missing data before performing a longitudinal mixed-model analysis (Twisk et al., 2013). Participants with missing data at some assessments will be included in the analysis and results will be modeled on the basis of the available data. For all analyses, researchers will use the standard  $p < 0.05$  criterion for determining statistical significance.

To test for faulty randomization, researchers will use chi-squared tests with Yates's continuity correction and t-tests with Welch's approximation of degrees of freedom and assuming unequal variance. If any effects are found, researchers will adjust for them using the confounding variable as a covariate in model testing and will note them in the interpretation of results. Researchers will also use these tests to check for differential dropout.

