#### *Study process*

Participants will first complete the PHQ-4 measure, which will determine if they are offered a \$10 gift card for their participation in the study in the study information portion. After participants read the study information and agree to participate, they complete baseline self-report measures of mental health outcomes and demographics. Next, they complete the intervention (see Materials section below for intervention information). After completing the intervention, participants are offered access to a browser and PDF version of the intervention they completed to keep and/or share with others. They are also referred to other online resources for people struggling with mental health. Next, they complete a few brief measures of hope, agency, meaning in life, and engagement with the intervention platform. 4 and 8 weeks later, they receive links via email to complete follow-up measures of mental health outcomes and engagement. At the end of the 8-week follow-up, participants are given access to all three conditions in PDF and browser forms. The entire study is conducted using the secure online experience management platform Qualtrics and several anti-fraud / bot measures are included in the survey. All contact between researchers and participants is asynchronous.

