#### *Additional analyses*

1. Duplicate the main analysis with the subset of participants who did not meet criteria for struggling with distress and thereby participated in the study without being compensated.
2. Duplicate the main analysis comparing the change in distress from baseline to week 4 follow-up rather than to week 8.
3. Duplicate the main analysis with the subset of participants who completed the week 8 follow-up.
4. Duplicate the main analysis but with the following covariates included in the mixed-effects model: gender (multiple choice), age (continuous), ethnicity (categorical), sexual orientation (categorical), education level (categorical), socioeconomic status (continuous), and if participants completed the study on a computer, tablet, or phone.
5. Use a one-way ANOVA to test between-group differences in distress at 8-week follow-up. If the omnibus ANOVA produces a significant F-score, researchers will conduct two planned contrasts to compare the experimental condition to each other condition, and will

compute Cohen's ds of these comparisons. Researchers will run the same ANOVA on the 4-week follow-up data and at post-intervention for outcomes collected then. Researchers will also conduct these ANOVAs on secondary outcomes.

6. Calculate Cohen's d effect sizes reflecting within-group intervention effects on distress for each condition from baseline to 4-week and 8-week follow-ups.
7. Run four logistic regression models with dropout as the outcome baseline measures as predictors to determine if they predict which participants drop out either before completing the intervention, before the post-intervention questions, or before the 4- and 8-week follow-ups.
8. Duplicate the main analysis including data from suspected bots/scammers.

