#### *Additional analyses testing exploratory hypotheses*

1. To test if demographic and baseline mental health characteristics predict one's willingness to choose a certain kind of content, researchers will conduct a separate multiple logistic regression for each kind of content one can choose in the content selection portion of the *blu surfer* program. Researchers define a "kind" of content as a topic (eg, emotional support, motivation, personal experience) or format (eg, video, image, article, activity). As demographic predictors, researchers will include age, gender, ethnicity, country, education level, employment status, socio-economic status, and having received professional mental health support in the past. As baseline mental health predictors, researchers will include distress, self-efficacy, hopelessness, meaning and purpose in life, adaptive actions and thought, and loneliness.
2. To test if the kinds of content one chooses predict change in distress over 8 weeks, researchers will conduct an MLM regression with each kind (defined as in the above analysis) as a binary predictor, study timepoint as another predictor, and the interaction between selected kind and timepoint as predictors, as well as a participant identifier as a random intercept.
3. To test how many pieces of content one adds when they pull content from an annotated library vs when they find it independently online, researchers will conduct a t-test of numbers of content added to one's guide across the "blu surfer" and "online help seeking as usual" conditions.

4. To test if participants are more satisfied in the *blu surfer* condition than the *online help seeking as usual* condition, researchers will conduct a t-test comparing mean satisfaction across those conditions.
5. To test if participants are more likely to view their mental health resource guide when they choose content from a curated library than when they select it all on their own, researchers will conduct a t-test comparing the mean number of times participants viewed their guide across the *blu surfer* and *online help-seeking as usual* conditions at 8 weeks after creating the guide.
6. To evaluate how age moderates change in distress over 8 weeks among participants completing popular online content interventions, researchers will conduct a mixed effects model with distress as the outcome, age, timepoint, and their interaction as predictors, and a participant identifier as a random intercept.

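### In all three studies, significance tests of baseline balance both declare faulty randomisation and choose the model covariates; they cannot identify a fault, and they leave the covariate set open until the data are seen

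*Combined protocol and SAP*

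**What the plan says.** The rule stands under Missing data handling in each study.

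- **Studies 2 and 3.** To look for faulty randomisation, "researchers will use chi-squared tests on demographic and outcome variables with Yates's continuity correction and t-tests with Welch's approximation of degrees of freedom". The action on a positive result is mandatory: "If any faulty randomization effects are found, researchers will adjust for them using the confounding variable as a covariate in model testing".
- **Study 1.** The same tests are named, but no variables are listed. The action is the same: "If any effects are found, researchers will adjust for them using the confounding variable as a covariate in model testing".
- **Threshold.** For all analyses the p < 0.05 "criterion will be used to determine statistical significance" (Studies 2 and 3; Study 1 sets the same level). No multiplicity control is given for the balance tests.
- **Primary model.** In each Main analysis section it is time by condition with a random intercept per participant and no covariates.
- **Pre-listed covariates.** A model with a fixed covariate list exists only under Additional analyses (item 3 in Study 1, item 4 in Studies 2 and 3).

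The same balance tests are also used to check for differential dropout.

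**The concern.** A baseline balance test asks whether the arms differ by more than chance would produce. If allocation was random, the answer is already known: among all randomised participants, any p < 0.05 is a chance finding. The rule nevertheless treats it as evidence of a fault and will have it reported as one.

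The analysed set adds a second source of imbalance. The Inclusion criteria sections drop participants on information that arises after randomisation, such as a statement at the end that they did not take part seriously, or a judgement of fraud. One listed sign of fraud is identical feedback about the intervention. Such exclusions can differ by arm, and the resulting imbalance would also be labelled faulty randomisation.

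The rule also leaves the model open. Variables enter because they happened to be imbalanced, not because they predict the outcome. The plan does not say whether an added covariate enters as a main effect or also interacts with time. Nor does it say what happens if the flagged variable is the baseline value of the outcome, which is already a response in the model.

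**Working it through.** The plan states no number of balance tests and no error rate for this rule, so there is no figure to reproduce. Three questions were checked.

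**1. How many tests?** This is an assumption built from variables that the plan names.
- Arms: three per study. In Studies 2 and 3, after week 8 "participants are given access to all three conditions in PDF and browser forms"; Study 1 says the equivalent.
- Demographics in the covariate rerun: "gender (multiple choice), age (continuous), ethnicity (categorical), sexual orientation (categorical), education level (categorical), socioeconomic status (continuous"), plus device, which makes 7.
- Further demographics in the Study 2 content-choice regression: "age, gender, ethnicity, country, education level, employment status, socio-economic status, and having received professional mental health support in the past". This adds country, employment and past support, so 3 more.
- Baseline outcome scales: 6 in Study 2 ("distress, self-efficacy, hopelessness, meaning and purpose in life, adaptive actions and thought, and loneliness"), 6 in Study 1 (Table 1) and 7 in Study 3 (Table 5).

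Study 2 therefore has 6 + 7 = 13 variables, or 16 with the further demographics. Study 3 has 14, or 17. A deliberately narrow list of 10 takes six scales plus age, gender, ethnicity and education.

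**2. How often is a correctly randomised study flagged?** For k independent tests the probability is 1 − 0.95^k. The simulation used 1,000 runs per setting, 100 per arm, correlation 0, 0.3 or 0.5 among the scales, and categorical variables with 2 to 5 levels. The pairwise column runs three Welch t-tests per continuous variable and one three-arm chi-squared test per categorical variable.

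| Variables | Formula | Simulated, one test each | Simulated, pairwise t-tests |
|---|---|---|---|
| 10 | 0.40 | 0.37–0.40 | 0.60–0.64 |
| 13 | 0.49 | 0.43–0.50 | 0.66–0.73 |
| 14 | 0.51 | 0.48–0.54 | 0.69–0.78 |
| 16 | 0.56 | 0.52–0.58 | 0.72–0.78 |
| 17 | 0.58 | not run | not run |

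Monte Carlo standard error is at most √(0.5 × 0.5 / 1,000) = 0.016. A separate run gave 0.40, 0.45 and 0.55 (one test each) and 0.56, 0.68 and 0.75 (pairwise) for 10, 13 and 16 variables. That sets the lower end of the pairwise range at about 0.55.

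**3. What does a flag do to inference?**

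*Primary test, complete data.* If covariate x enters as a main effect, its term γx is the same at every visit for a participant. It cancels from week 8 minus baseline, so the time-by-condition estimate cannot move. The simulated change was 0 to rounding error.

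*Primary test, 40% missing at random at each follow-up.* Adding x moved the week-8 interaction by a mean of 0.010 and at most 0.024 over 20 runs, against a standard error of 0.17. That is 0.010 / 0.17 ≈ 0.06 and 0.024 / 0.17 ≈ 0.14 standard errors. Over 2,000 trials per setting (three arms of 100, within-person correlation 0.6, pairwise trigger), the largest single shifts were 0.37 to 0.74 standard errors. Size, without and then with test-then-adjust:

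| Flagged covariate | Complete data | 40% missing |
|---|---|---|
| r = 0.5 with outcome | 5.0%, 5.0% | 4.5%, 4.45% |
| r = 0.7 with outcome | 5.6%, 5.6% | 5.0%, 5.1% |
| Baseline outcome itself | 5.2%, 5.2% | 4.7%, 5.2% |

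Monte Carlo error is about 0.5 points, so these sizes are near nominal.

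*Single-timepoint comparison.* With two arms of 100 and 20,000 trials, test-then-adjust had size 4.8%, 4.3% and 3.7% for r = 0.3, 0.5 and 0.7 (3.6% at r = 0.7 in a repeat). Always adjusting gave 4.9% to 5.0%. This matches the follow-up ANOVAs in form, not the primary model.

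**The case against.** The base formula is fixed, the trigger is written down in advance, and a pre-listed covariate rerun offers a sensitivity check. That stands, but writing down a data-driven rule does not fix the covariates. Three stronger readings are tempting, and the documents do not support them.

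- **That a correctly randomised study will more often than not be flagged.** This depends on a count the plan does not give. With one test for each of 10 variables the probability is about 0.4, and with 13 or 14 it is near one half. The primary hypotheses each compare two named arms, so running all three pairs is an inference. It is a reasonable one, because Welch's t-test is a two-group test and Yates's correction is meant for 2 × 2 tables.
- **That the primary test loses its nominal error rate.** The conservative size belongs to single-timepoint comparisons. The planned time-by-condition test stayed near 5% in every setting checked.
- **That every significant imbalance is chance.** This holds for all randomised participants if the randomiser works. It need not hold for the analysed set, where exclusions after randomisation can create real differences. Looking at balance there is useful; calling the result a randomisation fault is not justified.

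**Conclusion.** The point holds as a defect of specification and labelling. As written, the rule can report a randomisation fault that did not occur and leaves the covariate set to be chosen by imbalance.

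- **How often:** about 0.37 to 0.58 per study with one test per variable (10 to 17 variables), and about 0.55 to 0.78 with pairwise t-tests (simulated for 10 to 16 variables). Both assume 100 per arm, two-sided tests and working randomisation. The variable list is inferred from the plan, most loosely for Study 1.
- **Effect on the primary test:** none with complete data and a main-effect covariate. With missing follow-up, single estimates can move but size stays near nominal. The checks took missingness as random and did not cover a covariate interacting with time.
- **Effect elsewhere:** follow-up ANOVAs would be somewhat conservative (about 4.3% at r = 0.5 and 3.6% to 3.7% at r = 0.7), if the rule is applied to them. The plan does not say whether model testing includes them.

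The change should be made because it is cheap, not because the primary result is at serious risk.

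**What to change.** In Missing data handling of all three studies:

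1. Delete the sentences that test for faulty randomisation and adjust for what is found. State that no balance test changes any model.
2. Keep the primary model as written. Make the planned covariate rerun (Additional analyses, item 3 in Study 1, item 4 in Studies 2 and 3) the only adjusted analysis, limited to baseline covariates. Study 1's list includes whether a written-response question was answered, which may be recorded after randomisation and would then drop out.
3. Show baseline characteristics by arm without p-values, once for all randomised participants and once for the analysed set. A difference between the two tables points to the exclusions.
4. Check the randomiser against its configured allocation and its log. The document text gives no allocation ratio to compare arm counts with.
5. Restate the differential-dropout tests in their own sentence, because the present text defines them only by reference to the balance tests.

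The cost is wording and one extra table. The downside is that an imbalanced covariate outside the pre-listed set would not be adjusted for; that list holds demographics and device but no baseline outcome scales.

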#### *Additional analyses*

1. Duplicate the main analysis with the subset of participants who did not meet criteria for struggling with distress and thereby participated in the study without being compensated.
2. Duplicate the main analysis comparing the change in distress from baseline to week 4 follow-up rather than to week 8.
3. Duplicate the main analysis with the subset of participants who completed the week 8 follow-up.
4. Duplicate the main analysis but with the following covariates included in the mixed-effects model: gender (multiple choice), age (continuous), ethnicity (categorical), sexual orientation (categorical), education level (categorical), socioeconomic status (continuous), and if participants completed the study on a computer, tablet, or phone.
5. Use a one-way ANOVA to test between-group differences in distress at 8-week follow-up. If the omnibus ANOVA produces a significant F-score, researchers will conduct two planned contrasts to compare the experimental condition to each other condition, and will

compute Cohen's ds of these comparisons. Researchers will run the same ANOVA on the 4-week follow-up data and at post-intervention for outcomes collected then. Researchers will also conduct these ANOVAs on secondary outcomes.

6. Calculate Cohen's d effect sizes reflecting within-group intervention effects on distress for each condition from baseline to 4-week and 8-week follow-ups.
7. Run four logistic regression models with dropout as the outcome baseline measures as predictors to determine if they predict which participants drop out either before completing the intervention, before the post-intervention questions, or before the 4- and 8-week follow-ups.
8. Duplicate the main analysis including data from suspected bots/scammers.

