#### *Additional analyses*

1. Researchers will duplicate the main analysis with the subset of participants who did not meet criteria for struggling with loneliness and thereby participated in the study without being compensated.
2. Researchers will duplicate the main analysis with the subset of participants who completed the week 8 follow-up.
3. Researchers will duplicate the main analysis but will include the following covariates in the mixed-effects model: gender (multiple choice), age (continuous), ethnicity (categorical), sexual orientation (categorical), education level (categorical), socioeconomic status (continuous), if participants completed the study on a computer, tablet, or phone, and whether participants answered at least one written-response question.
4. Researchers will use a one-way ANOVA to test between-group differences in loneliness at 8-week follow-up. If the omnibus ANOVA produces a significant F-score, researchers will conduct two planned contrasts to compare the experimental condition to each other condition, and will compute Cohen's ds of these comparisons. Researchers will run the same ANOVA on the 4-week follow-up data. Researchers will also conduct these ANOVAs on secondary outcomes and at post-intervention for outcomes collected then.
5. Researchers will calculate Cohen's d effect sizes reflecting within-group intervention effects on the loneliness for each condition from baseline to 4-week and 8-week follow-ups. They will also do so for each secondary DV

6. Researchers will run four logistic regression models with dropout as the outcome baseline measures as predictors to determine if they predict which participants drop out either before completing the intervention, before the post-intervention questions, or before the 4- and 8-week follow-ups.

*Additional analyses testing exploratory hypotheses*

1. To compare change in mental health outcomes across presence of an insight experience, researchers will conduct a mixed-effects model with loneliness as the outcome, timepoint, insight experience, and the interaction between the two as predictors, and a participant identifier nested within experimental condition as a random intercept.

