### *Main analysis*

The main analysis compares change in distress from baseline to 8-week follow-up across experimental conditions. Researchers will use a mixed-effects model predicting distress with condition, measurement time point (1 = baseline, 2 = 4-week follow-up, 3= 8-week follow-up), and the 2-way interaction between condition and measurement time point as IVs and a participant identifier as a random intercept. Using the “lme4” package in R, this analysis will take the following form:

```
lmer(distress ~ time*condition + (1|study_id))
```

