### *Inclusion criteria*

Main analyses will be limited to only those participants who 1) met criteria for struggling with distress, 2) were randomized to a condition (ie, those who consented to participate and completed the baseline measures), 3) did not indicate that they did not participate seriously at the end of the study, 4) completed the study only once, and 5) were not clearly bots, responding mischievously,

or speeding past most of the content. Researchers will examine whether a response is fraudulent on a case-by-case basis, taking the suspicious factors mentioned in study 1's inclusion criteria into account.

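### The dropout models have no condition term, so they cannot tie selective dropout to an arm and can miss it when different kinds of people leave different arms; the separate differential-dropout check is too loosely specified to close the gap

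*Combined protocol and SAP*

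**What the plan says.** **Dropout models.** Study 2, Additional analyses, item 7: "Run four logistic regression models with dropout as the outcome baseline measures as predictors to determine if they predict which participants drop out". Study 1 (item 6) and Study 3 (item 7) say the same: "Researchers will run four logistic regression models with dropout as the outcome baseline measures as predictors". The four models are four stages of leaving, not four arms: "drop out either before completing the intervention, before the post-intervention questions, or before the 4- and 8-week follow-ups". Baseline measures are the only predictors named. Condition is not one of them, because the Inclusion criteria describe those analysed as people who "were randomized to a condition (ie, those who consented to participate and completed the baseline measures", so assignment follows baseline.

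**Separate check.** Under Missing data handling, chi-squared tests with Yates's correction and Welch t-tests are planned to look for faulty randomization. Study 1 then adds "Researchers will also use these tests to check for differential dropout", and Studies 2 and 3 add "These tests will also be used to check for differential dropout". None of the studies states which groups or variables are compared for dropout. The covariate-adjustment rule is tied to faulty randomization, and no action is stated for a positive dropout test.

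**Main model.** Study 2 uses "lmer(distress ~ time*condition + (1|study_id", closed by two brackets. It has a random intercept, no further baseline covariates and no imputation. Studies 1 and 3 use the same form for loneliness.

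**Covariate rerun.** Study 1 item 3 and Studies 2 and 3 item 4 add demographics, socioeconomic status and device (Study 1 also adds whether a written question was answered). Baseline self-efficacy and symptom scores are not listed, and no time interactions are stated.

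**The concern.** The primary question in each study is a contrast between arms. Dropout that works the same way in every arm, at the same rate, leaves that contrast largely intact. Dropout that removes one kind of person from one arm and another kind from another arm can distort it. A model pooled over arms answers the first question (who leaves?) and not the second (do different people leave different arms?). If selection runs in opposite directions, the pooled slope can be close to zero while the arms that remain are no longer comparable.

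This is plausible here. In Study 1 one arm has three sessions spaced a week apart and the others have one. In Study 2 one arm offers an annotated library and another asks for 25 minutes of unaided browsing. The exploratory hypotheses of all three studies expect baseline self-efficacy to predict improvement, yet self-efficacy is outside the main model. A baseline variable that drives both leaving and change, and that the model does not contain, is what produces bias under an available-data analysis.

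At stake is a report of no selective dropout alongside a week-8 difference that is partly an artefact of who stayed.

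**Working it through.** The documents give no sample size, dropout rate or effect size for this point, so there is no figure to reproduce. Every input below is an assumption, chosen to show a range.

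**1. Size by formula.** Let a baseline score X (mean 0, SD 1) shift the week-8 outcome by b SD per SD. Let the log-odds of dropout be a + sX in one arm and a − sX in the other, so that rates are equal. Among those who stay, the difference between arms in mean X is D = 2·|E(X | stay)|, and an unadjusted week-8 comparison is biased by b × D.
- a = −0.2, s = 0.8: dropout 46% in each arm, E(X | stay) = ∓0.32, D = 0.64. With b = 0.3, bias = 0.3 × 0.64 = 0.19 SD.
- Dropout 40%, s = 0.4: D = 0.31. With b = 0.15, bias = 0.15 × 0.31 = 0.05 SD.
- If X is the baseline outcome itself, b is its correlation with week 8. With D = 0.64, that gives 0.6 × 0.64 = 0.38 SD, or 0.5 × 0.64 = 0.32 SD.

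**2. Simulation.** Two arms, true effect zero, outcome SD 1, three visits with visit as a category. Correlation was 0.6 throughout (equal) or 0.7/0.5 (decaying). The slope was 0.8 and b was 0.3 for a score outside the model. Bias comes from 200,000 per arm with the planned random-intercept form. Detection comes from 400 trials at 100 and at 200 per arm, two-sided 0.05.

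| Dropout pattern | Pooled model flags | Condition × baseline flags | Rates by arm (chi-squared) | Welch by arm among stayers | Mixed-model bias, SD | Week-8 ANOVA bias, SD |
|---|---|---|---|---|---|---|
| A. On baseline outcome, opposite by arm | 3-4% | 100% | 3-5% | 94-100% | 0.00 (equal), 0.09 (decaying) | −0.33 to −0.38 |
| B. On another score that predicts change, opposite by arm | 2-4% | 100% | 5-6% | 96-100% | −0.17 to −0.18 | −0.19 to −0.20 |
| C. Same direction, unequal rates (33% v 59%) | 99-100% | 5-6% | 94-100% | 14-23% | about −0.04 | about −0.05 |
| D. Same direction, equal rates | 100% | 4-6% | 4% | 4-6% | within 0.01 | within 0.01 |

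A Welch test of leavers against stayers pooled over arms flags A and B in only 2-5% of trials. The ANOVA biases agree with the formula in step 1.

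**3. Smaller slopes.** With 150 per arm, about 40% dropout and opposite slopes of 0.4-0.8, the pooled model flags 3-5%, chi-squared on rates 3-5%, and the interaction 91-100%. A Welch test by arm among stayers flags 55%, 87% and 99% at slopes of 0.4, 0.6 and 0.8.

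**4. Does entering the score help?** With 41% dropout, slopes ±0.4-0.8 and b = 0.15-0.30, the mixed-model bias is 0.04-0.18 SD as planned, 0.03-0.16 SD with the score as a main effect only, and under 0.01 SD once its time interaction is added. The planned covariate rerun states no time interactions, so it would leave most of this bias even if the score were on its list.

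**The case against.** Three stronger readings are tempting, and the documents do not support them.

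*That both planned checks must pass while the arms differ.* The tests named for differential dropout are the same ones used for arm balance at baseline, and a t-test compares scores rather than rates. One natural reading is that baseline scores are compared by arm among those remaining, which finds the pattern in 55-100% of trials in the settings above. The text does not commit to that reading, so the defect is underspecification and not a shown failure.

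*That such dropout necessarily biases the primary result.* In Study 2, distressed people leaving one arm is dropout on the baseline primary outcome. That score is in the mixed model, so the dropout is missing at random given the model, and bias is about zero if the random-intercept covariance is right. Nor is this the only harmful pattern. Pattern C also biases the contrast, and there the interaction term is silent while the planned checks respond.

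*That pooled models cannot detect arm-specific selection at all.* The near-chance detection rates depend on mirrored slopes. With 150 per arm, the pooled model flags selection in one arm only (slopes 0 and 0.8) in 85% of trials, slopes of 0.2 and 0.8 in 98%, and −0.2 and 0.6 in 31%. What it cannot do in any of these is say which arm is responsible.

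It is also fair that item 7 states a descriptive aim, and that a covariate rerun is planned. The rerun does not cover self-efficacy or symptom scores. A description of who leaves is also of limited use in a randomised comparison if it is silent about arm.

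**Conclusion.** The concern holds in a limited form. As written, the dropout models in all three studies cannot attribute selective dropout to an arm, and they can miss it when selection runs in opposite directions. The companion tests close the gap only under one of several readings, and nothing follows from a positive result.

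Under the assumptions shown, the mixed-model week-8 contrast can be biased by about 0.04-0.18 SD when the selecting variable is outside the model and predicts change. Dropout on the baseline primary outcome alone gives little or no bias in the mixed model if its covariance is right (0.09 SD under the decaying correlation assumed), but about 0.33-0.38 SD in the unadjusted week-8 ANOVA. The sizes depend entirely on assumed dropout and slopes. The absence of a condition term is a matter of text. No baseline-only model, with or without interactions, can detect dropout that depends on unobserved outcomes.

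This is a worthwhile, inexpensive improvement and does not invalidate the main analysis.

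**What to change.** 1. In the dropout models of each study, add condition and condition-by-baseline terms for a short fixed list: the baseline primary outcome, the other main score (DASS-9 in Studies 1 and 3, ULS-3 in Study 2), GSE-6 and age. Use one joint test of the interactions. Do this at least for the week-4 and week-8 stages, where counts allow.
2. State that the differential-dropout tests compare, by arm, both dropout rates and the baseline scores of participants who remain. Keep the rate comparison, because the interaction does not see pattern C.
3. Beside the main result, report a sensitivity rerun of the main model with these baseline measures and their time interactions. The baseline primary outcome is already in the model as a response, so in practice the other three are added. Reporting this rerun whatever the tests show also supplies the action that the plan lacks.

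Cost: with three arms, condition takes 2 degrees of freedom and four interactions take 4 × 2 = 8, about 10 per dropout model, plus one extra model run per study. All the measures are already collected. Early-stage dropout counts are unknown and may be too small for the full set of terms.
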